3.5.4 ECG

Other than the summary table of ECG for one of the secondary endpoints, ECG values will be listed.

3.5.5 Other Safety Assessments

Other safety assessments such as hospitalizations and physical examinations will be listed.

4 DATA MONITORING COMMITTEE

An independent DMC composed of experts external to the sponsor and investigators will monitor the safety of trial participants and the conduct of the trial on an ongoing basis and will be responsible for the IA and recommendations regarding sample size re-estimation. Consistent with US Food and Drug Administration (FDA) recommendations (FDA Guidance for Industry, Establishment and Operation of Clinical Trial Data Monitoring Committees, 2006), the DMC will include at least 2 external clinicians with expertise relevant to the evaluation of COVID-19, such as Critical Care, Pulmonology, or Infectious Disease, as well as at least 1 independent biostatistician with expertise in clinical trial design and statistical methods for clinical research and analysis of research data including interim analysis. Details on the composition of the DMC and the schedule and format of DMC meetings and data outputs are provided in the DMC charter. The DMC will review, at a minimum, data for the sentinel subjects prior to continued

study drug dosing and cumulative safety data at regular intervals based on subject enrollment. The safety evaluations will be detailed in the DMC charter and will include review of conventional safety variables, such as serious adverse events. Any safety event that requires unblinding will be immediately reported to the DMC and to the FDA. The DMC may request and review any additional reports outside of the planned analyses at any time if deemed necessary to ensure the safety of subjects. The DMC will also review the efficacy data at the IA and make recommendations based on the futility criteria and for sample size re-estimation if needed (see Section 8.9). After reviewing study data, the DMC will make recommendations regarding continuation, termination, or modification of the study. The DMC may also perform ad hoc review of PK of subjects who require dialysis.

5 ANALYSIS TIMING

5.1 Interim Analysis

An IA will be conducted after 206 subjects have been enrolled (approximately 103 in each of the losmapimod and placebo arms) and have been treated for 14 days with 28 days of follow-up. Only futility—and potential sample size-estimation—will be assessed by the DMC at the IA. The O'Brien-Fleming group sequential method will be used to adjust alpha and beta for interim testing. Table 2, Figure 1, Figure 2, and Figure 3 contain sample size requirements, boundary information, and stopping probabilities for testing futility on the primary endpoint at both the IA and final analysis. P -values are single-sided. Sample size estimation was done using SAS® (Proc SeqDesign, Version 4.0). The study will not be stopped for efficacy at the IA.

5.1.1 Futility Testing

The process is as follows:

1. Futility at IA: If standardized z-value (MLE: maximum likelihood estimate) of $p_t - p_c$ is ≥ -0.67873 (-0.04017), or p-value ≥ 0.24865 , then stop for futility. Probability of stopping for futility under null hypothesis is ~ 0.75 .
2. At Final Analysis: The final p-value is tested at an adjusted alpha of 0.02784.

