3 STATISTICAL METHODOLOGY

3.1 General Considerations

3.1.1 *Analysis Day*

Analysis day will be calculated from the date of first dose of study drug. The day of the first dose of study drug will be Day 1, and the day immediately before Day 1 will be Day -1. There will be no Day 0.

3.1.2 *Definition of Baseline*

Baseline is defined as the last measurement prior to the first dose of study drug.

3.1.3 *Summary Statistics*

Categorical data will generally be summarized with counts and percentages of subjects. The denominator used for the percentage calculation will be clearly stated. Continuous data will generally be summarized with descriptive statistics including n (number of non-missing values), mean (with its standard error), first quartile, median, third quartile, standard deviation, minimum, and maximum.

Where appropriate, descriptive statistics may be presented with 95% CI.

3.1.4 *Hypothesis Testing*

All statistical comparisons will be made using one-sided tests at $\alpha = 0.025$. All null hypotheses will be of no treatment difference, and all alternative hypotheses will be one-sided. Confidence intervals will be 2-sided with $\alpha = 0.05$ and reported to the same precision as the applicable summary statistic (e.g., mean), and standard error will be reported to one additional decimal place. P-values will be reported to four decimal places, with p-values less than 0.0001 reported as "<0.0001".

3.1.5 *Type I Error for Testing Key Study Endpoints*

The overall Type I error of the study will be controlled at 0.025 for 1-sided tests of hypotheses for the following key study endpoints, using a closed test procedure. The key endpoints will be tested in the fixed sequence procedure as the same sequence they are listed below. Assuming the analysis of the prior endpoint yields statistically significant treatment effect, the next key endpoint will be tested.

1. Proportion of progressors to death or respiratory failure by Day 28
2. Change in clinical status using the 9-point WHO scale at Day 14
3. Change in clinical status using the 9-point WHO scale at Day 7
4. Oxygen-free days by Day 28

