3.4 Efficacy Assessment

3.4.1 Primary Efficacy Endpoint

3.4.1.1 Primary Analysis

The primary efficacy endpoint is the proportion of subjects who progress to death or respiratory failure by Day 28.

Respiratory failure is defined as either need for mechanical ventilation (invasive or non-invasive) or high flow oxygen (defined by greater than 15 LPM flow of oxygen to maintain oxygen saturation between 90% and 95%), sustained for at least 48 hours, at any time during the study.

The fitted logistic regression model is used to predict the response rate for every subject in the study as if they had received the treatment or the control intervention.

Assuming p_t is probability of outcome in the losmapimod arm; p_c is the probability of outcome in the control arm

Study hypothesis: $H_0: p_t - p_c = 0$

$H_1: p_t - p_c < 0$

Assuming $p_t=0.18$, $p_c=0.30$, we can restate the hypothesis as

$H_0: \theta = \theta_0 = 0$

$H_1: \theta = \theta_1 = -0.12$

where θ is calculated as $p_t - p_c$. For the final analysis, the proportion of subjects achieving the primary endpoint in the treatment arms will be compared using an adjusted risk difference obtained from the logistic regression model, adjusted for stratification factors, sex, and baseline CRP. Sample SAS codes are provided in Appendix A. More details can be found in Guo et al. (2012) and Ge et al. (2011).

An interim analysis to assess futility analysis—and potential sample size re-estimation—will be conducted, as discussed in Section 5.1.

All results will be summarized descriptively by treatment arm and expressed as proportions, along with corresponding unadjusted/adjusted 95% CI of the difference between response rates, and p-values.

In the first step of multiple imputation, data will be multiple imputed using the FCS discriminant function separately by treatment arm to 20 imputed datasets. This analysis assumes data are missing at random. The imputation model will include the stratification factors, sex, baseline CRP, and a two-level binary factor (discharge from the hospital prior to discontinuing the study; Yes, No). [REDACTED]

For each imputed dataset, the proportion of subjects achieving the primary endpoint in the treatment arms will be compared using an adjusted risk difference obtained from the logistic regression model, adjusted for stratification factors, sex, and baseline CRP for each imputed dataset.

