The estimated treatment effect and associated standard errors from each imputation from the 20 logistic regression model will be combined using Rubin's rules to provide an overall treatment effect, associated 95% confidence interval (CI), and 2-sided p-value. Sample codes are listed below.

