3.4.2 Secondary Efficacy Endpoints

Clinical status at Day 7 and Day 14:

Change in clinical status between baseline and at Days 7 and 14 will be modeled using ordinal logistic regression models, adjusting for stratification factors, sex and baseline CRP. If the subject progresses to death and the value of WHO 9-point scale is missing, the missing value of WHO 9-point will be imputed as (8) death.

Percentages for each category of the ranking scale will be tabulated by treatment arm, along with differences between treatment arms at each time point. The proportion of subjects for each of the items in the scale will be compared using an adjusted risk difference obtained from an ordinal logistic regression model, adjusting for stratification factors, sex and baseline CRP.

Total number of study days by Day 28:

(a) Free of oxygen supplementation; (b) in ICU; (c) of hospitalization; (d) free of respiratory failure; (e) alive; For each endpoint (a) – (e), a Poisson regression model will be used to assess

the relationship with treatment, adjusting for stratification factors, sex, baseline CRP and number of days on study. The key study endpoint of “oxygen free days by Day 28” will be tested at 1-sided significance level of 0.025 as outlined in Section 3.1.5.

If a patient died, the number of days of (a)-(e) are considered as having the events on and after the patient died. For example, if a patient died on Day 6. The days from Day 6 and after are considered not free of oxygen supplementation, hospitalization, ICU, and respiratory failure.

Percentage of subjects discharged from the hospital by Day 28:

Percentages of subjects discharged from the hospital will be tabulated by treatment arm, along with differences between treatment arms. The proportion of subjects will be compared using an adjusted risk difference obtained from a logistic regression model, adjusting for stratification factors, sex, and baseline CRP.

The percentage of subjects discharged from the hospital is defined as the number of subjects discharged from the hospital divided by the sum of the number of subjects who completed the study and the number of subjects who died during the study period.

A sensitivity analysis will be performed by excluding the subjects who died after being discharged from the hospital from the numerator of the above percentage calculation.

Missing data will be imputed similarly as primary endpoint for the above endpoints.

All-cause mortality at Day 28:

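### The SAP gives two final test levels for the primary endpoint, one-sided 0.025 in 3.1.4 and 0.02784 in 5.1.1, and does not say which governs

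*SAP*

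**What the plan says.** **General rule, SAP 3.1.4.** "All statistical comparisons will be made using one-sided tests at" 0.025, and "Confidence intervals will be 2-sided with" alpha 0.05. No endpoint is excepted.

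**Multiplicity, SAP 3.1.5.** "The overall Type I error of the study will be controlled at 0.025 for 1-sided tests of hypotheses", with four key endpoints tested in fixed sequence, the primary first. The next endpoint is tested if the one before it is statistically significant; the level for that decision is not given.

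**Primary analysis, SAP 3.4.1.1.** Results are summarised with the "unadjusted/adjusted 95% CI of the difference between response rates", and the multiple-imputation result with an "associated 95% confidence interval (CI), and 2-sided p-value".

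**Final analysis, SAP 5.1.1.** "At Final Analysis: The final p-value is tested at an adjusted alpha of 0.02784". Protocol 8.9.1 says the same. SAP Table 2 and protocol Table 6 give the matching boundary, z = -1.91358, under a footnote that sets overall one-sided alpha at 0.025. SAP 5.1 states that these p-values are one-sided.

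**Futility.** SAP 5.1.1 and 5.1.2 say the study stops if the interim statistic falls in the acceptance region. The word binding does not appear. SAP 5.1 says that the O'Brien-Fleming "group sequential method will be used to adjust alpha and beta for interim testing"; protocol 8.9 says beta only.

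**The concern.** The final primary result has one p-value and two levels to compare it with. An unqualified rule for all comparisons points to 0.025, and a rule specific to the final analysis points to 0.02784. SAP section 6, which lists changes from the protocol, does not mention the difference. If the p-value fell between the two levels, someone would have to choose the rule after unblinding. That choice would decide whether the trial met its primary endpoint and whether the other three key endpoints could be tested. The 95% interval reported beside the result would include zero, because it corresponds to 0.025 and not to 0.02784.

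A second question follows. A final level above 0.025 is affordable only because trials that cross the futility boundary can no longer reject. If 0.02784 is the intended level, that dependence should be written down.

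**Working it through.** **Inputs.** SAP Table 2: interim boundary z = -0.67873 (difference -0.04017) at 103 per arm; final boundary z = -1.91358 (difference -0.08009) at 205 per arm. SAP 3.4.1.1: rates 0.18 and 0.30, difference -0.12. SAP 5.1.2: re-estimation when conditional power is at least 50% and below 80%, maximum 820 subjects.

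**1. Reproduce the plan's figures.** The standard errors implied by Table 2 are 0.04017/0.67873 = 0.05918 and 0.08009/1.91358 = 0.04185. The information fraction is (0.04185/0.05918)² = 0.500. The expected z-values under the alternative are -0.12/0.05918 = -2.028 and -0.12/0.04185 = -2.867. With (Z1, Z2) bivariate normal and correlation √0.5:

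- Null: P(Z1 < -0.67873 and Z2 < -1.91358) = 0.02500, so acceptance is 0.97500, as in Table 2.
- Alternative: power is 0.800, and the probability of a futility stop is 0.0887 (Table 2: 0.08871).
- Φ(-1.91358) = 0.02784.

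So 0.02784 is the nominal final level that spends exactly 0.025 when the futility stop is enforced.

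**2. Type I error at each level.** The re-estimation rows integrate over Z1. They assume conditional power under the observed trend, the smallest sample size from 205 to 410 per arm that reaches 80% (410 if none does), and the conventional final statistic.

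| Final level | Design | Stop enforced | Stop ignored |
|---|---|---|---|
| 0.02784 | fixed N = 410 | 2.50% | 2.78% |
| 0.02784 | with re-estimation | 2.44% | 2.72% |
| 0.025 | fixed N = 410 | 2.26% | 2.50% |
| 0.025 | with re-estimation | 2.21% | 2.45% |

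At 0.02784 with re-estimation, 2.5% is passed only if more than about (0.02500 - 0.02444)/(0.02724 - 0.02444) = 0.20 of the crossings are overruled.

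**3. Power.** With the stop obeyed, power is 80.0% at 0.02784 and 79.0% at 0.025. With the stop ignored, it is 83.0% and 81.8%.

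**4. The disputed band.** One-sided p between 0.025 and 0.02784 means z between -1.95996 and -1.91358. At 205 per arm the observed difference lies between -1.95996 × 0.04185 = -0.0820 and -0.0801. With the stop obeyed, the probability of landing there is:

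- 0.18 v 0.30: 0.7999 - 0.7899 = 0.0100, about 1.0%
- 0.22 v 0.30: about 1.5%
- no effect: 0.02500 - 0.02263 = 0.00237, about 0.24%

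**5. Matching interval.** 1 - 2 × 0.02784 = 0.9443, a two-sided 94.4% interval.

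**The case against.** The best defence is that a specific rule overrides a general one. The 0.02784 is labelled an adjusted alpha, tabulated in both documents and repeated in protocol 8.9.1, while 3.1.4 is one sentence under general considerations. On that reading only a cross-reference is missing. This has force, and it is why keeping 0.02784 is a sound option. But the reader has to supply the precedence, and the 95% interval in the primary analysis still matches the other level.

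Several stronger readings are tempting, and the documents do not support them.

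- **That 0.02784 breaches the overall 0.025 of SAP 3.1.5.** It does not: it delivers 0.025 under the stop that 5.1.1 and 5.1.2 make mandatory.
- **That the 95% interval is a second success criterion.** It is a reported summary; no text decides success by it.
- **That SAP 3.4.2 confirms 0.025 for the primary.** Its statement, "will be tested at 1-sided significance level of 0.025 as outlined in Section 3.1.5", concerns oxygen-free days only.
- **That the 2-sided p-value might be compared with 0.02784.** No text says so. SAP 3.1.4 makes comparisons one-sided, and Table 2 pairs 0.02784 with a one-sided z.
- **That SAP Table 3 shows a design without a futility stop, because its Unfavorable rows stay at 410.** The 20% in that row at 0.18 v 0.30 matches average conditional power (about 19.7%). It does not match rejection frequency with a stop (about 42%) or without one (about 54%). The simulation code is not in the available text.
- **That the 'or' in the DMC options (SAP 5.1.3, protocol 8.9.3) permits continuation after a crossing.** SAP 5.1.2 sends that case to the futility boundary. It is loose drafting only.

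**Conclusion.** The inconsistency is real and narrow. SAP 3.1.4 and SAP 5.1.1 set different levels for the same test, and no visible text settles which one decides the primary endpoint or opens the fixed sequence. The design as written does not inflate Type I error. An excess arises only if a stop written as mandatory is overruled, and the ceiling is 2.78% (2.72% with re-estimation).

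The chance that the difference matters is small, about 1.0% to 1.5% under the two effects examined. The consequence would be a disputed Phase 3 primary result, and the remedy is cheap. It should be fixed before the interim; it does not undermine the design.

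The figures rest on a normal approximation, the standard errors implied by Table 2 (also used at 0.22 v 0.30), the re-estimation rule assumed above, and an interval built from the same standard error as the test. The statement that nothing reconciles the two levels covers the visible text only; the code appendices are not in it.

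**What to change.** Choose one level for the primary endpoint before the interim. SAP section 1 has the plan finalised by then.

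**Option A: keep one-sided 0.02784.** State that the futility boundary is binding. Add to SAP 3.1.4 an exception for the primary endpoint that points to 5.1.1. Report the matching two-sided 94.4% interval in 3.4.1.1. Cost: SAP wording only, apart from any matching protocol clarification.

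**Option B: test at one-sided 0.025 with the 95% interval.** State that futility is non-binding for Type I error, which then stays within 2.5% whether or not the stop is followed. Change the level in SAP 5.1.1 and protocol 8.9.1. Change the final row of SAP Table 2 and protocol Table 6 to z = -1.95996 (0.02500), difference -0.08203, and stopping probabilities 0.97737 and 0.21005. Redraw Figures 1 to 3. Restate power as about 79% with futility obeyed. In SAP 5.1, say that only beta is adjusted, as in protocol 8.9. Cost: about one point of stated power and a protocol amendment, which protocol 10.3.1 requires to be submitted to the IRB/IEC.

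Under either option, report a one-sided p-value in SAP 3.4.1.1 so that it matches the test. Neither option raises the planned 410 subjects.

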5.1.2 Sample Size Re-estimation

The Chen-DeMets-Lan method (Chen et al 2004) will be used for unblinded sample size re-estimation, with IA futility stopping boundaries created using O'Brien-Fleming method, as described above. Wald conditional probabilities will be calculated using the actual observed proportion from both treatment arms.

The maximum sample size allowed is 820 subjects. Sample size will be increased only if the observed data at the IA are promising; that is, if the conditional power is $\geq 50\%$ and $< 80\%$. Sample size will be increased to ensure a target conditional power of at least 80%. See appendix A for sample SAS codes for the conditional power calculation.

There is only one IA, and conditional power at IA must lie between 50% and 80% for sample size re-estimation to be implemented. These 2 conditions ensure that the target Type I error of 2.5% is not exceeded by increasing sample size to meet the original target power (Chen et al 2004).

Sample size re-estimation will not be done in the following 2 instances:

- If conditional power is <50%, then sample size re-estimation will not be done, and decision on futility will be made based on boundary values from the O'Brien-Fleming method.
- If conditional power is $\geq 80\%$, then a sample size re-estimation will not be done, as the study will be considered sufficiently powered to detect the effect of interest at the final analysis.

A Wald Test statistic will be calculated and compared with the boundary value for futility (see Table 2). If the Wald Test statistic lies in the acceptance region then the study will stop for futility.

All calculations for the IA and the unblinded sample size re-estimation will be conducted by an external, unblinded statistician. The DMC will review the results in a closed session and make appropriate recommendations to the Sponsor afterwards.

Table 2: Boundary Values for Interim Analysis Futility Assessment

| Analysis Stage | Sample Size | | Beta: Futility | | | Alpha: Efficacy | | |
|------------------|-------------|---------|--------------------------|----------|--|--------------------------|-----|---|
| | Losmapimod | Control | Standardized-Z (p-value) | MLE | Stopping Probability (accept null under null hypothesis) | Standardized-Z (p-value) | MLE | Stopping Probability (accept null under alternative hypothesis) |
| Interim Analysis | 103 | 103 | -0.67873 (0.24865) | -0.04017 | 0.75135 | Not applicable | -- | 0.08871 |
| Final Analysis | 205 | 205 | -1.91358 (0.02784) | -0.08009 | 0.97500 | -- | -- | 0.20000 |

Overall alpha=0.025 (1-sided); overall power=80%.

Abbreviations: MLE: maximum likelihood estimate.

Figure 1 Acceptance Region (Standardized-Z Scale)

[figure not shown]

Figure 2 Acceptance Region (P-value)

[figure not shown]
[figure not shown]

Figure 3 Acceptance Region (Maximum Likelihood Estimate)

| | | Promising | 16% | 67% | 79% | 410 | 537 | 92% |
| | | Favorable | 58% | 96% | 96% | 410 | 410 | 96% |
| 0.2 | 0.3 | Unfavorable | 38% | 17% | 17% | 410 | 410 | 74% |
| | | Promising | 17% | 66% | 79% | 410 | 543 | 84% |
| | | Favorable | 44% | 95% | 95% | 410 | 410 | 91% |
| 0.22 | 0.3 | Unfavorable | 53% | 14% | 14% | 410 | 410 | 58% |
| | | Promising | 17% | 66% | 79% | 410 | 548 | 72% |
| | | Favorable | 30% | 95% | 95% | 410 | 410 | 82% |

Note: The simulation result is based on 10000 replications using SAS. See Appendix B for codes.

5.2 Final Analysis

Topline TFLs (Tables Figures and Listings) will be provided approximately 1 week after the study database is declared final. Final TFLs will be provided approximately 3 weeks after the study database is declared final. In addition to TFLs, SDTM (Study Data Tabulation Model) data and ADaM (Analysis Data Model) data along with associated files will be provided. Associated files may include annotated case report forms (CRFs), SDTM specifications, SDTM programs, ADaM specifications, ADaM programs, TFL programs, and Clinical Data Interchange Standards Consortium (CDISC) Define packages for both SDTM and ADaM data.

[figure not shown]
6 CHANGES FROM PROTOCOL-SPECIFIED STATISTICAL ANALYSES

[figure not shown]
The statistical analysis plan introduced the following modifications to the analyses planned in the protocol:

[figure not shown]
1. Per Protocol, the FAS will consist of all subjects who are randomly assigned to receive double-blind study drug. Due to limited data, the FAS is updated to consist of all subjects who are randomized and receive any study drug.
2. Due to limited data, considerations on adjusting the model covariates have been added in the SAP.

